3.7 Other Secondary Outcomes: Quality of Life

It is hypothesised that:

Very early aphasia therapy (UC-Plus and VERSE) will result in better quality of life at 12 and 26 weeks post stroke than UC control.

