3.7.2 Statistical Hypotheses for Quality of Life

The specified quality of life hypotheses involve the assessment of the following statistical hypotheses:

- 1. Very early daily aphasia therapy (UC-Plus or VERSE) will result in higher quality of life than Usual Care alone at 12 weeks post stroke.
- 2. VERSE aphasia therapy will result in higher quality of life than Usual Care alone at 12 weeks post stroke.
- 3. UC-Plus will result in higher quality of life than Usual Care alone at 12 weeks post stroke.
- 4. VERSE aphasia therapy will result in higher quality of life that UC Plus at 12 weeks post stroke.
- 5. Very early intensive aphasia therapy (UC-Plus or VERSE) will result in greater improvements in communication ability at 26 weeks post stroke.
- 6. VERSE aphasia therapy will result in higher quality of life than Usual Care alone at 26 weeks post stroke.
- 7. UC- Plus will result in higher quality of life than Usual Care alone at 26 weeks post stroke.
- 8. VERSE aphasia therapy will result in higher quality of life that UC Plus at 26 weeks post stroke.

3.7.1 Analysis Method:

Separate linear mixed effects regression model will be used to assess quality of life as measured by the SAQoL¹⁷ at 12 weeks post stroke and at 26 weeks post stroke. Each model will compare the effects of:

- 1. VERSE therapy to usual care alone
- 2. UC- Plus therapy to usual care alone

The model will adjust for baseline aphasia severity by including the WAB-R $(AQ)^2$ score at baseline as a covariate. Baseline stroke severity will be controlled for by including the NIHSS⁴ at baseline as a fixed factor in the model. Recruitment site will be included as a random effect. The treatment effects will be reported as difference in SAQoL¹⁷ (between VERSE and UC and between UC- Plus and UC); the corresponding 95% confidence intervals will be reported.

3.7.1.1 Handling of Missing Data:

Handling of missing data will be similar to the detail in section 3.5.3.

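### The quality-of-life analysis names only VERSE vs UC and UC-Plus vs UC; the pooled contrast that tests its stated hypothesis is specified nowhere, and one listed hypothesis is miswritten

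*SAP*

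**What the plan says.** Hypothesis 5 of section 1.2 and the opening of section 3.7 use the same statement: "Very early aphasia therapy (UC-Plus and VERSE) will result in better quality of life at 12 and 26 weeks post stroke than UC control".

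Section 3.7.2 expands this into eight statistical hypotheses, four per time point. At 12 weeks they are:
- the pooled comparison (item 1): "Very early daily aphasia therapy (UC-Plus or VERSE) will result in higher quality of life than Usual Care alone at 12 weeks post stroke"
- VERSE against UC (item 2): "VERSE aphasia therapy will result in higher quality of life than Usual Care alone at 12 weeks post stroke"
- UC-Plus against UC (item 3): "UC-Plus will result in higher quality of life than Usual Care alone at 12 weeks post stroke"
- the two intensive arms against each other (item 4): "VERSE aphasia therapy will result in higher quality of life that UC Plus at 12 weeks post stroke"

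Items 6, 7 and 8 repeat items 2, 3 and 4 at 26 weeks. Item 5 stands where the 26-week pooled hypothesis would be expected, but reads: "Very early intensive aphasia therapy (UC-Plus or VERSE) will result in greater improvements in communication ability at 26 weeks post stroke".

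The Analysis Method after this list (numbered 3.7.1 for a second time) plans separate linear mixed models at 12 and 26 weeks. Each compares VERSE with UC and UC-Plus with UC, adjusted for baseline WAB-R AQ and NIHSS, with site as a random effect. The reporting sentence has the same limit: the SAQoL differences to be reported are those "between VERSE and UC and between UC- Plus and UC); the corresponding 95% confidence intervals will be reported".

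**The concern.** The hypotheses and the analysis written for them do not match. The one quality-of-life hypothesis among the trial's aims concerns the two intensive arms together, and the Analysis Method does not name that comparison. An analyst who follows the text exactly would produce two arm-against-UC estimates per time point and nothing labelled as the test of the section 3.7 hypothesis.

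Someone would then have to decide, possibly after seeing the results, how two pairwise results answer one pooled question. The SAP gives no rule. Accepting either significant result makes a false claim more likely. Requiring both costs power. The pooled contrast avoids this choice and is more precise than either pairwise contrast, but the plan does not commit to it for SAQoL.

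**Working it through.** **Step 1. Match each listed hypothesis to a named contrast.**

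| Item | Contrast | Week | Named in the quality-of-life Analysis Method? |
|---|---|---|---|
| 1 | UC-Plus + VERSE vs UC | 12 | No |
| 2 | VERSE vs UC | 12 | Yes |
| 3 | UC-Plus vs UC | 12 | Yes |
| 4 | VERSE vs UC-Plus | 12 | No |
| 5 | Intensive arms pooled, on communication, no comparator | 26 | No (miswritten) |
| 6 | VERSE vs UC | 26 | Yes |
| 7 | UC-Plus vs UC | 26 | Yes |
| 8 | VERSE vs UC-Plus | 26 | No |

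Two contrasts at two time points give 2 × 2 = 4, which cover items 2, 3, 6 and 7. Three quality-of-life hypotheses (1, 4 and 8) have no named contrast, and item 5 is a wording error. If item 5 is read as the 26-week pooled quality-of-life hypothesis, it too has no named contrast.

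**Step 2. Look for the missing contrasts elsewhere in the SAP.**
- Pooling of the intensive arms appears in sections 3.5.2 and 3.5.4, tied to the primary 12-week communication hypothesis.
- A VERSE vs UC-Plus model is written in section 3.6.2.1 for %MPR and %CIUs only.
- Section 3.6.2.2 compares each intensive arm separately with UC at 26 weeks. So item 5 read literally, as a pooled communication hypothesis, has no analysis either.
- Section 3.1 says in general terms that differences among the three arms will be tested on all endpoints at the two-sided 5% level. This can be read to cover VERSE vs UC-Plus. It does not describe a pooled contrast.

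**Step 3. Illustrate what depends on the choice.** Section 1.7 gives no SAQoL effect size or SD and says no pilot data on quality of life existed, so the plan has no quality-of-life power figure to reproduce. Assumptions: n evaluable per arm in all three arms (allocation is 1:1:1), equal SDs, the same true effect in both intensive arms, and normal test statistics. The pairwise powers of 60, 70 and 80% are assumed values.

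Standard errors:
- pairwise: SD × √(1/n + 1/n) = SD × √(2/n)
- pooled: SD × √(1/(2n) + 1/n) = SD × √(1.5/n)
- ratio: √(1.5/2) = 0.866

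Power of the pooled contrast: a pairwise test with 80% power has non-centrality 1.960 + 0.842 = 2.802. Dividing by 0.866 gives 3.235, and Φ(3.235 − 1.960) = Φ(1.275) = 0.899.

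The two pairwise statistics share the UC arm, so their correlation is (1/n)/(2/n) = 0.5. The last column below is the bivariate normal probability that both exceed 1.960.

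| Pairwise power | Pooled contrast | Both pairwise tests significant |
|---|---|---|
| 60% | 72% | 44% |
| 70% | 82% | 56% |
| 80% | 90% | 69% |

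Under the null, with the same correlation:
- at least one of the two tests is significant in the favourable direction: 4.5%, against 2.5% for a single test
- at least one is significant in either direction: 9.1%, against 5%

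**The case against.** A reader might infer that half of the listed hypotheses have no model and cannot be answered, or that the pooled contrast has been discarded. The SAP does not support that. The natural reading of the Analysis Method is one model per time point holding all three arms. VERSE minus UC-Plus, and the average of the two intensive-arm effects relative to UC, are then linear combinations of coefficients already estimated. Nothing excludes the pooled contrast. Item 1 shows that it was intended, and the primary analysis gives a precedent for pooling. Section 3.1 gives general authority for VERSE vs UC-Plus. Item 5 is a drafting slip and should not be counted as a plainly unanalysed quality-of-life hypothesis.

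The figures also have limits. The pairwise powers are illustrative. The SAP states neither an either-arm nor a both-arms rule. The hypothesis is directional, so 4.5% against 2.5% is the fairer comparison than 9.1% against 5%. Section 3.1 openly leaves Type I error for secondary analyses unadjusted, so the error rate alone is not an oversight.

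All of this stands, and it narrows the point without removing it. That a contrast can be estimated does not commit anyone to report it, and the specific reporting sentence omits both. The precedent in section 3.5.2 is confined to the primary hypothesis. Leaving secondary tests unadjusted does not say which result answers the pooled question.

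**Conclusion.** The concern holds as an inconsistency between the hypotheses and the analysis of a secondary outcome. The Analysis Method names and reports two of the four contrasts at each time point. The pooled SAQoL contrast, which is the test of the stated aim, is specified nowhere in the SAP. VERSE vs UC-Plus is covered only in general terms, and item 5 is miswritten. These statements rest on the text alone.

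The size of the consequence is illustrative and depends on the equal-arm, equal-SD and equal-effect assumptions. If the effects in the two intensive arms differ, the power figures change. The standard-error ratio and the null error rates do not depend on the effects.

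The primary analysis, the sample size of 246 and their conclusions are unaffected. The correction should be made because a stated aim otherwise has no designated test, and the change is nearly free.

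**What to change.** In the quality-of-life Analysis Method, specify one three-arm SAQoL model per time point with the covariates and random site effect already planned. Pre-specify and report, with 95% confidence intervals:

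1. UC-Plus and VERSE pooled vs UC, named as the test of the section 3.7 hypothesis, stating whether it is formed by merging the arms as for the primary outcome or by averaging the two arm effects
2. VERSE vs UC (already planned)
3. UC-Plus vs UC (already planned)
4. VERSE vs UC-Plus

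Reword item 5 of section 3.7.2 as pooled early therapy vs UC on quality of life at 26 weeks.

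Cutting hypothesis 5 of section 1.2, section 3.7 and the list in 3.7.2 back to the two contrasts now planned would also restore consistency, but would give up the pooled aim.

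The cost is SAP wording and two further contrasts per time point. No new data are needed and the sample size does not change. The form of the pooled contrast should be fixed before the allocation is unblinded for analysis.

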3.8 Other Secondary Outcomes: Cost Effectiveness

It is hypothesised that:

Very early intensive aphasia therapy (UC-Plus and VERSE) will be more cost-effective than Usual Care at 26 weeks post stroke.

3.8.1 Analysis Method:

Details of the cost effectiveness analyses will be published separately and are not included here. Results from the effectiveness analyses will be the same for describing the effectiveness component of the incremental cost effectiveness calculation.

3.9 Secondary Outcomes: Safety Important Medical Events (IME) Adverse Events (AE) and Serious Adverse Events (SAE)

Important Medical Events (IMEs), Adverse Events (AEs) and Serious Adverse Events (SAEs) are defined in the main trial protocol. These are expected to be rare occurrences. Aphasia therapy is not expected to have an effect on these events. Therefore, no formal hypotheses have been stated about these outcomes. All IMEs, AEs and SAEs will be reported by therapy group.

As rare events, counts of IMEs, AEs and SAEs are expected to have a Poisson or negative binomial distribution. The distributions of these events will be modelled and appropriate generalised linear mixed models will be developed to assess differences between groups if the data suggests that there is a between-group difference of greater than 3 standard deviations in any of these event types.

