1.10.2 Secondary Outcome Measures

The secondary outcome measures include effectiveness, quality of life, safety and cost effectiveness measures. These are:

- Communication improvement at 26 weeks, assessed as %MPR¹⁹ at 26 weeks
- Improvement in connected speech at 12 and 26 weeks on discourse measures¹⁰⁻¹⁶
- Quality of life measured by the Stroke and Aphasia Quality of Life (SAQOL)¹⁷ scale
- Depression measured at 12 and 26 weeks by the Aphasia Depression Rating Scale (ADRS)¹⁸
- Adverse Events and serious adverse events as defined in the trial protocol
- Cost effectiveness of VERSE and UC-Plus therapies compared to Usual Ward Care. The economic analysis will be outlined separately in an Economic Analysis Plan

2 Funding

This study is funded by the National Health and Medical Research Council (NHMRC), Australia (Project Grant Number 1044973), The Tavistock Trust for Aphasia, United Kingdom and Edith Cowan University, Australia. The funders of this study have no influence on the study design, data collection, data interpretation, writing of the protocol or statistical analysis plan.

3 Statistical Plan

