3.1 Analysis principles and general considerations

- All outcomes and analyses are prospectively characterised as primary or secondary.
- Differences in all endpoints between the three arms of the trial (VERSE, UC-Plus, UC) will be tested independently at the two-tailed 5% significance level. All estimates of treatment effects will be presented with 95% confidence intervals.
- No formal adjustments will be undertaken to constrain the Type I error associated with planned secondary or exploratory analyses. The information provided by analyses is designed to supplement the evidence from the primary analyses; it will provide a more complete characterization of the treatment effects.
- The analyses for all outcome measures (effectiveness, quality of life and safety) will be conducted on an intention the treat (ITT) basis i.e. all patients will be analysed as members of the group to which they were randomised, irrespective of whether they received the allocated treatment or not. The ITT strategy for VERSE is based on the following principles:
 - All available outcome data are collected on all randomised patients.
 - All participants are analysed in the groups to which they are randomised.
 - All available outcome data will be used in the primary analyses. The primary analyses will be reported without missing data imputed.
 - A separate analysis with missing data imputed will also be reported. Missing data will be assumed to be missing at random (see section 3.5.3)
 - A sensitivity analysis including all randomised individuals will be conducted. The sensitivity analysis will consider alternative assumptions about data missing not at random (MNAR) (see section 3.10).
- A per-protocol analysis will be conducted separately, but will not be included in the primary results for this trial. The per-protocol analysis will be described in greater detail when it is published. However, it will be based on the following principles:
 - The per-protocol cohorts will be based on whether or not participants received the planned minimum 15 hours of direct aphasia therapy as the intervention dose.
 - The per-protocol cohort will include:
 - VERSE participants who receive at least 15 hours of direct language therapy over the intervention period;
 - UC-Plus participants who receive at least 15 hours of direct language therapy over the intervention period;
 - All UC participants who are randomised to the UC group.

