3.2 Interim Analysis and Stopping Rules

There are no formal interim analyses planned for this trial. The DSMC periodically reviews data for the primary outcome measure and safety, and will advise the chair of the Executive committee if, in their view, the randomised comparisons have provided both (i) 'proof beyond reasonable doubt' that very early aphasia rehabilitation (VERSE and UC-Plus groups) is clearly indicated or clearly contraindicated because of safety concerns and (ii) evidence that might influence future patient management. The DSMC are guided by Haybittle-Peto boundaries in making this determination. That is, they work on the principle that a difference of at least 3 standard errors in the analysis of effectiveness or serious adverse events (e.g. death from all causes, aspiration pneumonia within the first 50 days post stroke) may be needed to justify halting, or modifying the study before the planned recruitment is completed.

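### Section 3.9 compares safety between arms only when the observed gap exceeds an undefined 3 standard deviations, which conflicts with the testing rule in section 3.1 and leaves most safety differences without an estimate or interval

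*SAP*

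**What the plan says.** Section 1.10.2 includes among the secondary outcomes "Adverse Events and serious adverse events as defined in the trial protocol".

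Section 3.1 sets the general rule: "Differences in all endpoints between the three arms of the trial (VERSE, UC-Plus, UC) will be tested independently at the two-tailed 5% significance level". It adds: "All estimates of treatment effects will be presented with 95% confidence intervals". A separate item in 3.1, on intention to treat, names safety among the outcome measures to be analysed.

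Section 3.9 handles safety differently. It says of these events: "These are expected to be rare occurrences". It expects no effect of aphasia therapy on them and so states no formal hypotheses. One output is unconditional: "All IMEs, AEs and SAEs will be reported by therapy group". The comparison is conditional: "appropriate generalised linear mixed models will be developed to assess differences between groups", but only "if the data suggests that there is a between-group difference of greater than 3 standard deviations in any of these event types".

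The Table 6 shell in Appendix 1 has count columns for each arm and overall, with no column for an effect estimate or interval.

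The only other threshold of 3 in the SAP is in section 3.2, where the data safety monitoring committee is guided by "a difference of at least 3 standard errors" when considering whether to halt or modify the trial early.

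**The concern.** Three things are wrong with the condition.

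- **It conflicts with 3.1.** One section commits to testing every endpoint between arms at 5%. The other withholds the comparison for a listed secondary outcome unless the data already look extreme. An analyst cannot follow both.
- **It is not defined.** A standard deviation could be that of events per patient, of an arm's total count, or of the estimated difference (a standard error). The arms to be compared are not named either. The readings give very different triggers.
- **It depends on the result.** Whether a safety effect is estimated turns on its observed size. Model estimates that get through the gate are therefore too large on average. Smaller differences appear as bare counts with no statement of the excess risk they are compatible with.

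The stake is the final safety report. Therapy starts the day after a baseline assessment made 2 to 14 days after stroke, and section 3.2 names death and aspiration pneumonia as examples of events the committee watches. A table of counts without intervals does not tell a reader how much harm the data can exclude.

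**Working it through.** **Inputs.** From the SAP: 82 participants per arm, 246 in total (section 1.7); 1:1:1 allocation (1.4); two-sided 5% level (3.1); trigger of 3 (3.9). The SAP gives no event rates and derives no figure from the 3.9 rule, so there is nothing of its own to reproduce. The risks below are assumptions shown as a range.

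**Step 1: how strict is 3 standard errors?** Two-sided p = 2 × [1 − Φ(3)] = 0.0027. Against the 0.05 of section 3.1 this is 0.05/0.0027 ≈ 18.5 times stricter.

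**Step 2: which observed doublings pass?** For x vs 2x patients with an event, 82 per arm, use the pooled statistic z = (x/82)/√[p̄(1 − p̄)(2/82)] with p̄ = 3x/164. For x = 12: p̄ = 36/164 = 0.2195, standard error 0.0646, z = 0.1463/0.0646 = 2.26. For the doublings that would not be modelled, the last column gives the risk ratio and interval that 3.9 would leave out.

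| Patients with an event | z | Modelled under 3.9? | Risk ratio (95% CI) |
|---|---|---|---|
| 4 vs 8 | 1.20 | no | 2.0 (0.63-6.38) |
| 8 vs 16 | 1.77 | no | 2.0 (0.91-4.41) |
| 12 vs 24 | 2.26 | no | 2.0 (1.07-3.72) |
| 16 vs 32 | 2.75 | no | 2.0 (1.19-3.35) |
| 18 vs 36 | 2.99 | no | 2.0 (1.24-3.22) |
| 19 vs 38 | 3.12 | yes | |

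The intervals use √(1/x − 1/82 + 1/2x − 1/82) as the standard error of the log risk ratio. At 12 vs 24, p = 0.024: a difference by the 5% rule of 3.1, yet not modelled under 3.9. With an unpooled standard error the boundary moves by one patient: at 18 vs 36, z = 0.2195/√[(0.2195 × 0.7805 + 0.4390 × 0.5610)/82] = 3.08.

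With the two intensive arms combined (164 vs 82), a doubled risk first passes at 16 of 82 vs 64 of 164 (z = 3.08). For Poisson event counts in two arms of 82, z = x/√(3x), which equals 3.00 at 27 vs 54, so more events than that are needed.

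**Step 3: how large must the other arm's risk be?** Solve (p1 − p0)/√[p1(1 − p1)/82 + p0(1 − p0)/82] = 3. For p0 = 10%, p1 = 27.9% (2.8-fold). For p0 = 5%, p1 = 20.1% (4.0-fold).

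**Step 4: how often does a true doubling trigger?** Exact binomial enumeration with the pooled statistic, 82 per arm:

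| True risks (assumed) | Passes 3 SE | Passes two-sided 5% |
|---|---|---|
| 5% vs 10% | 2% | 22% |
| 10% vs 20% | 10% | 43% |
| 15% vs 30% | 24% | 64% |
| 20% vs 40% | 42% | 81% |

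The normal approximation for 10% vs 20% has standard error √[(0.09 + 0.16)/82] = 0.0552, and 1 − Φ(3 − 0.10/0.0552) = 12%; the same approximation at the 5% level gives 44%.

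**Step 5: selection.** Over the enumerated 10% vs 20% trials that pass 3 SE, the mean observed risk difference is 19.5 points, against a true 10.

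**Step 6: the other readings of standard deviation.**
- *Events per patient.* With a Poisson mean of 0.5, 3 × √0.5 = 2.1 extra events per patient, or (0.5 + 2.1)/0.5 ≈ 5.2-fold. The trigger is then practically out of reach.
- *The arm's total count.* With standard deviation √count, 9 vs 18 events is 9/√9 = 3.00 and 10 vs 20 is 10/√10 = 3.16. A doubling then passes from 10 vs 20 events.

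**The case against.** The best defence is that 3.9 is a deliberate exception. Events are expected to be rare, no effect is expected and no hypothesis is stated, so declining formal tests is reasonable. This stands as a reason to drop p-values. It does not justify making the estimate depend on the observed gap, and 3.1 makes no exception for safety.

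A reader might infer that even a doubling of deaths or serious adverse events would go uncompared. The documents do not support that without qualification:

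- Counts by arm are always reported, and with the arm sizes a reader could work out a crude risk ratio for deaths or any serious adverse event. Those counts are not selected, so the exaggeration in Step 5 applies only to the model output.
- On the 3-standard-error reading a doubling does trigger from 19 vs 38 patients, which a frequent category such as all adverse events might reach. On the √count reading it triggers much earlier.
- The event rates are assumed.

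A reader might also take the confidence-interval sentence in 3.1 as a promise of an interval for every safety endpoint. It governs how estimates are presented and does not itself require one for each endpoint. The sentence that conflicts with 3.9 is the one on testing all endpoints.

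Finally, the monitoring committee reviews unblinded safety data during the trial, and even a 5% test would have modest power for the rarer events (22% and 43% in the first two rows of Step 4). Both points limit the severity. Low power, though, argues for showing intervals.

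**Conclusion.** The point holds. Section 3.9 sets an undefined, result-dependent condition on the between-arm assessment of listed secondary outcomes and conflicts with the 5% testing rule in 3.1. Some readers may take 3.9 as modelling the event distributions in every case, but the between-group assessment is conditional on either reading.

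On the 3-standard-error reading with 82 per arm and a pooled statistic, observed doublings up to 18 vs 36 patients get no model. Under assumed risks of 10% and 20% the trigger is met about 10-12% of the time, with reported differences then about double the truth on average. These sizes rest on that reading and on assumed event rates. The lack of definition and the conflict between sections rest on neither.

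This should be fixed before the data are unblinded. It does not touch the primary analysis or data collection, and it does not mean that safety data go unreported.

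**What to change.** 1. In 3.9, delete the 3-standard-deviation condition.
2. Report unconditionally, for deaths and for participants with at least one serious adverse event, important medical event and adverse event, a risk difference or rate ratio with 95% confidence interval. Do this for the combined intensive arms vs UC, each intensive arm vs UC, and VERSE vs UC-Plus. Use exact, Poisson or negative binomial methods as the counts allow.
3. In 3.1, state that safety outcomes are estimated with 95% confidence intervals without formal hypothesis tests. Without this change the 5% testing sentence would still conflict with 3.9.
4. Leave the 3-standard-error guide in 3.2 as it is, for the monitoring committee only.
5. Add the estimates and intervals to Table 6 or a companion table.

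The cost is a wording change in two sections and a few extra rows of analysis. No new data are needed.
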